2.2 Trial Design

This is a Phase 2/3 (Phase 2b in the US), randomized, placebo-controlled, double-blind, multi-center trial designed to evaluate the efficacy and safety of 2 treatment regimens of CAM2029 versus placebo in patients with PLD. Approximately 69 patients will be randomized in the trial.

The trial consists of an up to 12-week Screening Period followed by a 52-week (12-month) Double-Blind Treatment Period for which patients will be randomized in a 1:1:1 ratio to 1 of the 3 treatment arms:

- Arm 1: CAM2029 10 mg once weekly
- Arm 2: CAM2029 10 mg every 2 weeks (weekly alternation with placebo)
- Arm 3: Placebo once weekly

Following completion of the Double-Blind Treatment Period, all patients will continue to a 120-week (30-month), open-label, single-arm, extension period with CAM2029 10 mg once weekly, followed by an 8-week safety follow-up period. The estimated duration of the trial for each patient is approximately 47 months.

A primary endpoint analysis will be performed when the last patient has completed the Double-Blind Treatment Period (Week 53).

An overview of the trial design is shown in [Figure 1](#).

[figure not shown]

Figure 1: Trial design

CL: clinical laboratory sampling; FU: follow-up; MRI: magnetic resonance imaging; N: number of patients; R: randomization

a Dose reduction to CAM2029 10 mg every 2 weeks will be allowed in the Extension Period.

The trial population is comprised of adult patients (≥ 18 years) who are diagnosed with PLD associated with ADPKD or isolated as in ADPLD, and who meet all the inclusion criteria and none of the exclusion criteria specified in Section 5 of the clinical trial protocol.

3 STATISTICAL HYPOTHESES

The primary objective is to assess superiority of treatment with CAM2029 compared to placebo on liver volume in patients with PLD.

The key secondary objective is to assess superiority of treatment with CAM2029 compared to placebo on patient-reported PLD-related symptoms.

In the analysis of the primary and key secondary efficacy endpoints, the primary comparison will be between the average effect of the 2 CAM2029 doses compared to placebo. In addition, the 2 doses of CAM2029 will be compared with placebo separately.

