8.9.3 Secondary Efficacy Endpoints

8.9.3.1 Key Secondary Efficacy Endpoint

The key secondary efficacy endpoint is change from baseline to Week 53 in the PLD-S measure score and this endpoint will be analyzed with the same methods as for the primary endpoint. In the analysis of the key secondary efficacy endpoint, the main comparison will be between the average effect of the 2 CAM2029 doses compared to placebo. In addition, the 2 doses of CAM2029 will be compared with placebo separately, see also [Section 8.10](#).

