3.1 Multiplicity Adjustment

Two doses of CAM2029 are analyzed in the trial. To protect the overall significance level, the following closed order testing procedure will be used:

1. The effect of the combined CAM2029 treatment groups compared to placebo on change in htTLV at Week 53
2. The effect of treatment with CAM2029 10 mg given once weekly compared to placebo on change in htTLV at Week 53
3. The effect of treatment with CAM2029 10 mg given every 2 weeks compared to placebo on change in htTLV at Week 53

Each test will be performed on the 5% significance level starting with the first test in the list and stopping the testing procedure at the first test for which the p-value is larger than 0.05.

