5.9.2.4 Supplementary Analyses

5.9.3 Key Secondary Efficacy Endpoint and Estimand

The estimand definitions applicable to secondary objectives are described in [Table 2](#).

[figure not shown]
The PLD-S is a PRO currently under development to assess patient reported symptoms of PLD. [REDACTED]

[figure not shown]
The key secondary efficacy endpoint is change from baseline to Week 53 in the PLD-S measure score and this endpoint will be analyzed with the same methods as for the primary endpoint. In the analysis of the key secondary efficacy endpoint, the main comparison will be between the average effect of the 2 CAM2029 doses compared to placebo. In addition, the 2 doses of CAM2029 will be compared with placebo separately as described in [Section 3.1](#).

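### PLD-S is a declared superiority hypothesis but is missing from the testing hierarchy: its alpha, its order and its gate from htTLV are not stated

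*SAP*

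**What the plan says.** SAP Section 3 names two superiority objectives. The first is liver volume. For the second it says: "The key secondary objective is to assess superiority of treatment with CAM2029 compared to placebo on patient-reported PLD-related symptoms". It treats both endpoints alike: "In the analysis of the primary and key secondary efficacy endpoints, the primary comparison will be between the average effect of the 2 CAM2029 doses", with placebo as the comparator, followed by each dose separately. That makes three comparisons per endpoint.

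SAP 3.1 then sets out an ordered procedure meant to control the overall level. It has three steps, all on htTLV. The first sets the pooled CAM2029 arms against placebo and the second the once-weekly arm against placebo. The third and last step reads: "The effect of treatment with CAM2029 10 mg given every 2 weeks compared to placebo on change in htTLV at Week 53". All three are tested at 5%, and testing stops at the first step that is not significant. Protocol 8.10 gives the same three htTLV tests. PLD-S appears in neither list.

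On PLD-S itself, SAP 5.9.3 says that "this endpoint will be analyzed with the same methods as for the primary endpoint" and that "the 2 doses of CAM2029 will be compared with placebo separately as described in" Section 3.1. Protocol 8.9.3.1 says "In addition, the 2 doses of CAM2029 will be compared with placebo separately" and points to protocol 8.10.

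**The concern.** The references from the PLD-S sections lead to lists that hold no PLD-S test. The primary-endpoint method that PLD-S inherits yields a reported p-value and a 95% confidence interval (SAP 5.9.2.2), so PLD-S p-values will exist. The readable text does not say at what level they are to be judged, in what order, whether a failed htTLV test blocks them, or whether they are nominal.

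PLD-S is the only patient-reported endpoint ranked above the other secondaries. If its place in the testing scheme is settled only after unblinding, a favourable symptom result cannot serve as confirmatory evidence, and an unfavourable one invites argument about which rule applied.

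**Working it through.** **Step 1: the plan's own figures.** Inputs from SAP Section 6 are a residual SD of 180 mL/m, 20 patients per arm and two-sided 5%. The standard error is 180·√(1/20+1/20) = 56.9 mL/m for one dose against placebo, and 180·√(1/40+1/20) = 49.3 mL/m for the combined comparison. Power comes from the noncentral t distribution.

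| Comparison | Noncentrality | Plan | Recomputed |
|---|---|---|---|
| 20 v 20, 165 mL/m | 165/56.9 = 2.90 | 80% | 80.6% |
| 40 v 20, 165 mL/m | 165/49.3 = 3.35 | about 90% | 90.8% |
| 40 v 20, 141 mL/m | 141/49.3 = 2.86 | about 80% | 80.3% |
| Smallest significant difference, 20 v 20 | – | about 115 mL/m | 115.2 mL/m |

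The design figures reproduce.

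**Step 2: the htTLV hierarchy alone.** With no effect, a false htTLV claim requires step 1 to reject, so the family error is that of one test at 5%. Simulation gives 5.0%. This part of the plan does what it says.

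**Step 3: two readings for PLD-S.** The text does not choose between them.

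- *Unordered:* combined, weekly and two-weekly comparisons are each tested at 5%.
- *Ordered:* the 3.1 order is copied within PLD-S, so the combined test comes first and gates the two dose tests.

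Neither reading includes a gate from htTLV, because none is written.

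The three contrasts share the placebo arm and are correlated. With equal arms, the combined contrast has variance 1.5/n, each dose contrast 2/n, and their covariance is 1.5/n. The correlation is therefore 1.5/√(1.5·2) = 0.87 between combined and either dose, and 1/2 = 0.5 between the two doses. The independence figure, 1 − 0.95³ = 14.3%, is thus too high for the unordered reading. Simulation was used instead: 1,000,000 trials, 20 per arm, pooled variance on 57 df, no effect on either endpoint. The chance of at least one false PLD-S claim is 9.6% unordered and 5.0% ordered.

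**Step 4: both endpoints together.** The documents give no correlation between htTLV and PLD-S, so 0 to 0.8 is assumed.

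| Assumed correlation | PLD-S unordered | PLD-S ordered |
|---|---|---|
| 0 | 14.1% | 9.75% |
| 0.5 | 13.3% | 9.1% |
| 0.8 | 12.0% | 7.9% |

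The first row can be checked by hand: 1 − 0.95·(1 − 0.0958) = 14.1% and 1 − 0.95² = 9.75%. Simulating 23 per arm gives nearly identical results.

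**Step 5: after repair.** If all six tests form one fixed sequence at 5%, the error over both endpoints is at most 5%. The price is the chance of getting as far as PLD-S. With the same true htTLV effect in both doses, SD 180 mL/m and 20 per arm, simulation gives:

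| True htTLV effect | PLD-S reached after all three htTLV tests | PLD-S reached after combined htTLV only |
|---|---|---|
| 165 mL/m | 70.7% | 90.8% |
| 141 mL/m | 53.7% | 80.2% |

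Power for PLD-S itself cannot be computed, because the documents give no PLD-S effect size or SD.

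**The case against.** A reader might infer that the plan runs three PLD-S tests at 5% each with no gate. No passage says so. The cross-reference in SAP 5.9.3, together with the instruction to use the primary endpoint's methods, can equally mean that the 3.1 order carries over to PLD-S. In that case PLD-S alone holds 5%, and the 9.6% and 12–14% figures do not apply. This objection stands: what the documents support is an unspecified rule, not a stated rule of three separate 5% tests.

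It can also be argued that PLD-S was never meant to be confirmatory. SAP 3.1 introduces the procedure by reference to the two doses, so it could concern dose multiplicity on the primary endpoint only. The protocol's objectives speak of evaluating an effect, not of superiority. The trial is Phase 2b in the US with partly exploratory aims (protocol 2.2), and PLD-S is still being developed and validated within this trial. This has weight, and it is why declaring the p-values nominal is a legitimate repair. It does not remove the gap. SAP Section 3 lists PLD-S superiority among the statistical hypotheses, and the SAP labels analyses as exploratory where it means that, as for subgroups in 5.9.6. PLD-S carries no such label.

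Finally, the key secondary estimand in SAP Table 2, part of 5.9.3 and the text under 5.14–5.15 are not visible. A statement on the status of PLD-S there cannot be excluded, and the missing text is not counted as a fault. SAP 3.1 and protocol 8.10 themselves show no redaction, and they agree.

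**Conclusion.** The gap is real. PLD-S is a declared superiority hypothesis whose references lead to a hierarchy that omits it, so the stated control of the overall level does not cover it. Under no effect on either endpoint, error across the two endpoints is about 12–14% on the unordered reading and 8–10% on the ordered one. It exceeds 5% on both because no htTLV gate is written. These ranges rest on the assumed correlation of 0 to 0.8. If all three htTLV effects are real, no false htTLV claim is possible and the error is that of PLD-S alone: 9.6% or 5%.

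A reader might also conclude that the primary result is compromised. It is not: the htTLV hierarchy holds 5%, and its power and the sample size of 69 are untouched. This should be fixed before database lock, but it is not a fault in the primary analysis.

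**What to change.** Extend SAP 3.1 and protocol 8.10. After the three htTLV tests, append PLD-S combined v placebo, then weekly v placebo, then every-2-weeks v placebo, each at two-sided 5% under the same stopping rule. State that any PLD-S p-value obtained outside the sequence is nominal. Correct the cross-references in SAP 5.9.3 and protocol 8.9.3.1 so that they point to these steps. SAP Section 2 allows changes until database lock and unblinding for the primary analysis.

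The cost is wording in two documents and no htTLV alpha. The real downside is that PLD-S cannot be claimed if any htTLV test fails: it is reached with probability about 71% at a true 165 mL/m in both doses, and about 54% at 141 mL/m. Placing PLD-S combined directly after htTLV combined would raise these to about 91% and 80%, but in a single sequence the htTLV dose tests would then depend on PLD-S.

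If the sponsor does not want a confirmatory PLD-S claim, the alternative is to declare all PLD-S p-values nominal, remove superiority from the key secondary objective in SAP Section 3, and correct the same cross-references.

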3.1 Multiplicity Adjustment

Two doses of CAM2029 are analyzed in the trial. To protect the overall significance level, the following closed order testing procedure will be used:

1. The effect of the combined CAM2029 treatment groups compared to placebo on change in htTLV at Week 53
2. The effect of treatment with CAM2029 10 mg given once weekly compared to placebo on change in htTLV at Week 53
3. The effect of treatment with CAM2029 10 mg given every 2 weeks compared to placebo on change in htTLV at Week 53

Each test will be performed on the 5% significance level starting with the first test in the list and stopping the testing procedure at the first test for which the p-value is larger than 0.05.

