8.2 Determination of Sample Size

In Hogan 2020, the comparison between pasireotide and placebo over 12 months resulted in a treatment difference in reducing htTLV of approximately 235 mL/m, or 9 to 10% expressed as percent change from baseline (50). The RSDs with the two analysis approaches were approximately 170 mL/m and 8%.

With 20 patients per treatment arm, the power is 80% if the true treatment difference is 165 mL/m (approximately 70% of the difference seen in the Hogan trial). This calculation is based on an assumed RSD of 180 mL/m using a t-test with a significance level of 5% (two-sided). With the same assumptions, the smallest observed treatment difference to give $p < 0.05$ is approximately 115 mL/m. If the 2 CAM2029 treatment arms are combined in the comparison to placebo, the number of patients in the comparison will be 40 versus 20. Assuming the same treatment difference, 165 mL/m, the power is approximately 90%. For a treatment difference of 141 mL/m, the power for the combined comparison would be approximately 80%.

With an assumed 15% drop-out rate the total number of patients required in the trial will be 69.

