8.10 Adjustments for Multiplicity

Two doses of CAM2029 are analyzed in the trial. In order to protect the overall significance level, the following closed order testing procedure will be used:

1. The effect of the combined CAM2029 treatment groups compared to placebo on change in htTLV at Week 53
2. The effect of treatment with CAM2029 10 mg weekly compared to placebo on change in htTLV at Week 53
3. The effect of treatment with CAM2029 10 mg every 2 weeks compared to placebo on change in htTLV at Week 53

Each test will be performed on the 5% significance level starting with the first test in the list and stopping the testing procedure at the first test for which the p-value is larger than 0.05.

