6 SAMPLE SIZE DETERMINATION

The sample size calculation is based on a trial by Hogan et al comparing pasireotide to placebo (2). In this trial, the comparison between pasireotide and placebo over 12 months resulted in a treatment difference in reducing htTLV of approximately 235 mL/m, or 9-10% expressed as percent change from baseline. The residual SDs with the 2 analysis approaches were approximately 170 mL/m and 8%.

With 20 patients per treatment arm, the power is 80% if the true treatment difference is 165 mL/m (approximately 70% of the difference seen in the Hogan trial (2)). This calculation is based on an assumed residual SD of 180 mL/m using a t-test with a significance level of 5% (two-sided). With the same assumptions, the smallest observed treatment difference to give $p < 0.05$ is approximately 115 mL/m. If the two CAM2029 treatment arms are combined in the comparison to placebo, the number of patients in the comparison will be 40 vs 20. Assuming the same treatment difference, 165 mL/m, the power is approximately 90%. For a treatment difference of 141 mL/min, the power for the combined comparison would be approximately 80%.

With an assumed 15% drop-out rate the total number of patients required in the trial was estimated to be 69.

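### The step from the weekly to the every-2-weeks test adds no error control and lowers the chance of a confirmatory every-2-weeks claim by an amount that depends on the true effects

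*SAP*

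**What the plan says.** SAP 3.1 lists three tests in a fixed order. Step 1 pools the two regimens: "The effect of the combined CAM2029 treatment groups compared to placebo on change in htTLV at Week 53". Step 2 takes the weekly arm alone against placebo on the same endpoint. Step 3 does likewise for the less frequent regimen. All three are done at 5%, "stopping the testing procedure at the first test for which the p-value is larger than 0.05". Protocol 8.10 has the same list and rule; its third entry reads "The effect of treatment with CAM2029 10 mg every 2 weeks compared to placebo on change in htTLV at Week 53". Neither document says why weekly comes before every 2 weeks.

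The combined test is the average of the two dose effects against placebo, taken from one three-arm ANCOVA (Protocol 8.9.2, SAP 5.9.2.2).

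On power, Protocol 8.2 says: "With 20 patients per treatment arm, the power is 80% if the true treatment difference is 165 mL/m". SAP 6 rests this on an "assumed residual SD of 180 mL/m using a t-test with a significance level of 5% (two-sided"). For the combined comparison, "the number of patients in the comparison will be 40 vs 20", and the power is put at about 90% for the same effect. No power is given for the third test as it stands in the sequence.

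**The concern.** Under the stopping rule, the every-2-weeks dose can be tested confirmatorily only if the weekly dose has succeeded. If weekly narrowly misses, a clear every-2-weeks result cannot carry a confirmatory claim, even when the combined test is significant. A restriction of that kind normally buys control of the familywise error. Here it appears to buy none, because the combined test has already done that work. At stake is the chance of a confirmatory statement on one of the two regimens the trial was set up to evaluate.

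**Working it through.** **Inputs.** 20 patients per arm, residual SD 180 mL/m, two-sided 5% t-test, effect 165 mL/m (Protocol 8.2, SAP 6); 1:1:1 allocation; average contrast with weights 0.5, 0.5, −1 (Protocol 8.9.2).

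**The plan's own figures.**
- One dose v placebo: SE = 180 × √(1/20 + 1/20) = 56.9; 165/56.9 = 2.90. On 38 df the power is 80.6% (stated: 80%).
- Combined, 40 v 20: SE = 180 × √(1/40 + 1/20) = 49.3; 165/49.3 = 3.35. Power 90.8% (stated: about 90%). At 141 mL/m: 80.3% (stated: about 80%).
- Smallest significant single-dose difference: 115.2 mL/m (stated: about 115).

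All reproduce.

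**Why the last link is not needed.** Call the true effects W (weekly) and E (every 2 weeks). The three nulls are (W + E)/2 = 0, W = 0 and E = 0. If any two hold, so does the third. The only intersection is therefore W = E = 0, and the combined test is a valid 5% test of it. By the closure principle, W = 0 may be rejected when the combined and weekly tests are both significant, and E = 0 when the combined and every-2-weeks tests are both significant. Neither dose has to wait for the other. The argument carries over to one-sided nulls: if neither dose is better than placebo, the average is not better either.

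**Familywise error by simulation** (2,000,000 trials per scenario, three arms of 20, pooled SD on 57 df):

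| True effects (mL/m) | Planned order | Combined, then each dose |
|---|---|---|
| Both zero | 5.0% | 5.0% |
| One zero, other 165 | 2.5% | 2.5% |
| One zero, other 2000 | 5.0% | 5.0% |
| +165 and −165 (average zero) | 5.0% | 5.0% |

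Testing both doses with no combined test in front would give 9.0% when both effects are zero. Step 1 is needed; the link from step 2 to step 3 is not.

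**What the link costs.** With a pooled SD, the combined t statistic is (t_W + t_E)/√3. If both dose statistics exceed the critical value c, the combined one exceeds 2c/√3 = 1.15c. Power at step 3 of the planned order is therefore the probability that both doses are significant. Without the link, it is the probability that the combined and every-2-weeks tests are significant. Simulated probability of a confirmatory every-2-weeks claim (simulation error about 0.1 point):

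| Weekly / every 2 weeks (mL/m) | Without the link | Planned order | Loss (points) |
|---|---|---|---|
| 165 / 165 | 80.2% | 70.8% | 9.4 |
| 165 / 165, 23 per arm | 85.7% | 78.1% | 7.6 |
| 141 / 141 | 66.1% | 53.8% | 12.3 |
| 165 / 141 | 67.4% | 61.1% | 6.3 |
| 165 / 115 | 50.6% | 47.1% | 3.5 |
| 165 / 82.5 | 29.5% | 28.3% | 1.2 |
| 200 / 165 | 81.1% | 78.3% | 2.8 |
| 235 / 165 | 81.3% | 80.8% | 0.5 |
| 120 / 165 | 75.7% | 50.0% | 25.7 |

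In the first row, the combined and every-2-weeks tests succeed and the weekly test fails in 9.4% of trials; those are the blocked claims. Separate two-arm t-tests in place of the pooled SD give 79.5% v 69.6%. Weekly power at 165/165 is 80.2% under both rules. The rule without the link rejects everything the planned order rejects, so it cannot lose power for either dose.

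**The case against.** The strongest defence is that nothing here is wrong. A fixed sequence is a legitimate closed test, it is pre-specified, and the two documents agree on it. Putting the higher-exposure regimen first is natural: Protocol 4.2.4 predicts that every-2-weeks exposure is half that of weekly dosing. If the effect follows exposure, the loss is small. The primary comparison is the combined one, which the order does not touch, and Protocol 2.2 describes the trial's aim as exploratory (Phase 2b in the US). All of this stands. It limits the size of the point, but it does not give the last link a purpose.

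A reader might also infer more than the documents support:

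- **That power falls from 80% to 71% whatever the truth.** That figure needs equal effects of 165 mL/m and 20 evaluable patients per arm. Equal effects are the plan's own simplification for the combined power, not a finding.
- **That the every-2-weeks dose goes unexamined if weekly fails.** Only confirmatory status is lost. Each dose is compared with placebo separately, and Protocol 8.3 provides for 95% intervals.
- **That the 80% in Protocol 8.2 is wrong.** It is correct for the single t-test it describes and is not presented as the power of step 3.
- **That the weekly arm will do worse through more discontinuations.** The documents give no differential rate, and Protocol 4.2.4 expects weekly dosing to be well tolerated. The 120/165 row shows sensitivity; it is not a forecast.
- **That every 2 weeks matters more because it is the extension regimen.** Protocol 4.1.3 and 6.1 give CAM2029 every 2 weeks in the extension; SAP 2.2 gives it once weekly, with reduction to every 2 weeks allowed. The documents disagree, so the point cannot rest on either.

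**Conclusion.** The point holds as an avoidable loss of power, not as an error-rate fault. The size depends on the true effects: 9.4 points in the planning case, about 0.5 to 6 points in the weekly-better scenarios examined (rising towards the equal-effect figure as the two effects converge), and about 26 points if weekly is clearly the weaker dose. These figures assume SD 180 mL/m, complete data on 20 patients per arm (except the row with 23) and a t-test in place of the imputation-based ANCOVA. The closure argument needs none of this; it needs only that the combined test is valid at 5%. Because the alternative keeps the same maximum error and never rejects less, there is no statistical reason in the documents to keep the link.

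**What to change.** Before database lock and unblinding, replace the stopping sentence in SAP 3.1 and Protocol 8.10 with: *If test 1 is significant at 5%, tests 2 and 3 are each performed at 5%, independently of each other.*

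This uses no alpha, patients or data. It does take a SAP revision, which SAP 2 allows until lock and unblinding, and a protocol amendment with approvals as required (Protocol 11.1 and 12.1). Time may be short: the SAP is based on a protocol dated 29-Jan-2025, and last patient first visit was planned for Q4 2023.

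If the order is kept on purpose, give the reason, and state in Protocol 8.2 and SAP 6 that power for the every-2-weeks test within the sequence is about 71% when both effects are 165 mL/m.

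Separately, the extension regimen in the protocol and in SAP 2.2 must be reconciled.
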